### Specific Aim 2: tDCS for depressive symptoms in mmTBI

Experiments in this aim will test the hypothesis that left prefrontal anodal tDCS in patients with mmTBI will significantly reduce depressive symptoms compared to sham stimulation. Aim 2.1: Patients will be assessed for symptoms of depression via self-report instruments and clinician-administered scales from NIH Common Data Elements before, immediately after, and one month after the stimulation protocol. Aim 2.2: Persistence of antidepressant benefit will be assessed via telephone interview at 6 months and one year. Aim 2.3: clinical predictors of tDCS response such as EEG frontal theta synchrony, injury severity, premorbid intelligence, neuroimaging abnormalities, and symptom burden will be determined.

## 2. Background

## PROTOCOL TITLE: Transcranial direct current stimulation for treatment of deficits after traumatic brain injury.

Traumatic brain injury (TBI) is a significant public health problem. An estimated 1.7 million TBI-related deaths, hospitalizations, and emergency department (ED) visits occur in the United States each year, costing an estimated \$76.5 billion in 2000 alone. Among 34 states in a 2004 survey New Mexico had the 2nd highest TBI fatality rate, with approximately 10,000 ED visits and 1400 admissions for TBI, making this an important regional problem to be addressed for our communities. Even after mild TBI, up to 22% of patients will report functional impairment at one year post-injury. Much of this loss of function is due to the fact that the majority of TBIs affect the frontal lobes and cause damage to the frontal-subcortical circuits that are responsible for the complex thought processes required to navigate contemporary life, including comportment and social behavior, mood and motivation, and especially cognitive control.

These deficits in cognition and emotion compound one another, as the neural circuits mediating them are closely interconnected. Within the first year after TBI 33% of patients will suffer a major depressive disorder, which may exacerbate any separate post-traumatic cognitive deficits and effectively render a “double-hit” to patients’ abilities to manage their lives’ daily activities. Conversely, deficits in the domain of cognitive control can be seen even after only mild TBIs, affecting executive functions such as response inhibition, working memory impairment, and set shifting and leading to further depression as patients spend long periods functionally disabled. Unfortunately, few effective treatments exist for the post-acute neurobehavioral sequelae of TBI. Current strategies for cognitive rehabilitation are both time- and resource intensive but yield only small effect sizes. Non-FDA approved treatments such as methylphenidate are coarse in their mechanism of action and carry adverse consequences such as irritability, addiction, and cardiovascular effects. Dopamine agonists have had mixed results in improving function after TBI, and little evidence currently exists to recommend any other class of medication. Treatment approaches for mood symptoms in TBI are understudied, nonspecific, and have even been shown to worsen cognition. Novel rehabilitation approaches that simultaneously and holistically address both the cognitive and emotional post-traumatic deficits of TBI are needed.

The current proposal represents a major step towards a solution for post-TBI symptoms that harnesses the intact brain’s neuroplastic potential to overcome a variety of deficits. Transcranial direct current stimulation (tDCS) is a non-invasive form of brain stimulation utilizing low amounts of current to modulate neuronal activity and improve neuropsychiatric symptoms across diverse disorders, including post-stroke aphasia and motor learning, working memory in dementia, and major depression. We will attempt to demonstrate that tDCS produces similar gains in cognitive symptoms among mmTBI patients as we have seen in our lab, as well as improvements in depressive symptoms others have found in depressed patients. We will then correlate response to tDCS with EEG measures of cognitive control and brain connectivity so as to better identify patients likely to benefit from tDCS, as well as clarify the mechanism of therapeutic action of tDCS. Due to its low cost, minimal side effects, and the ease with which it can be integrated with existing rehabilitation approaches, empirical support for tDCS would be a “game-changer” in the field of TBI. Successful completion of our specific aims will have a major impact on research and clinical practice regarding the management of debilitating TBI symptoms. Toxic effects of medications could be avoided; visits to rehabilitation facilities could be reduced; and treatment could be provided in diverse settings. Future studies would elucidate optimal electrode placements and stimulation parameters for specific cognitive symptoms and in specific types of brain injury, as well as provide a rational mechanism of therapeutic action in terms of improved functional brain connectivity. Integration with emerging multimodal neuroimaging techniques may reveal exactly which type of patient benefits from which type of tDCS, personalizing clinical interventions.

### Review of relevant literature

*tDCS can improve brain function.* Anodal tDCS typically has an excitatory neuronal effect due to a shift toward depolarization, while cathodal stimulation elicits a hyperpolarization. tDCS-induced changes last from minutes to hours, and multiple stimulation sessions over the course of days to weeks can lead to cumulative long-lasting effects. This powerful neuroplastic effect of tDCS has

PROTOCOL TITLE: Transcranial direct current stimulation for treatment of deficits after traumatic brain injury.

already been applied to injured brain in patients recovering from stroke, with observed benefits in motor control, neglect, vision, and aphasia, without adverse consequences such as seizures or worsening of deficits. Anodal stimulation of the dorsolateral prefrontal cortex (DLPFC) has become a standard protocol in the cognitive tDCS literature because of its ability to improve multiple dimensions of cognitive functioning, including cognitive control and working memory, attention, improved decision making, and enhanced memory. Reduction of impulsivity has been demonstrated with anode over right DLPFC.

*tDCS is understudied in TBI.* Application of this therapy to TBI is a logical next step, but tDCS has not been extensively studied in this disorder as it has for stroke rehabilitation and depression. Several animal studies have shown that anodal tDCS is potentially neuroprotective after brain injury. Only three studies have attempted tDCS for cognition in TBI, all utilizing left prefrontal anodal stimulation. Angelakis et al. treated 5 severe TBI patients with 5 days of anodal 1 mA tDCS for 20 minutes then 5 days of 2 mA. Age of injury ranged from 6 months to 10 years, and electrode positioning was at left DLPFC or left sensorimotor cortex (C3) in alternating order. There were no adverse events, and no clear advantage from either electrode position. Three patients of the five experienced benefit by 1 year followup.

Kang et al, in a one-session protocol involving 9 patients with moderate-severe TBI 2-18 months from date of injury, administered 2mA tDCS for 20 minutes while they performed a computerized cognitive rehabilitation program. Significant benefits in set-switching and reaction time were detected immediately after and up to 24 hours later. There were no adverse events and the treatment was well tolerated, despite all subjects having known left frontal lobe pathology. In contrast, Lesniak et al. administered tDCS at 1 mA for 10 minutes to 23 TBI patients for fifteen sessions over a 3-week protocol. All patients had severe TBI between 4 and 92 months from date of injury, 16 of whom had known left frontal pathology. Their group found the treatments safe and well tolerated, but failed to find any significant benefit in a multitude of attentional domains. Our correspondence with studies registered in clinicaltrials.gov for tDCS in TBI (Spaulding, NYU, U. Leige) did not discover any occurrence of seizures or serious adverse events.

We conclude the following from these studies: (1) anodal tDCS over left DLPFC at various current densities, durations, and over multiple sessions in TBI patients of moderate and severe degree is safe; (2) the presence of pre-treatment brain abnormalities, even at the site of anodal electrode, does not necessarily increase risk nor impede benefit, and (3) the severity of injury and current density/stimulation protocol used may influence the efficacy of tDCS.

*Choice of study population.* Our research strategy is focused on the mild to moderate range of TBI severity. Importantly, this range of severity captures the vast majority of TBI patients. Though we believe patients with severe injuries may also benefit from tDCS, we are concerned that their greater burden of neuropathology may compromise plasticity. Our research strategy calls for patients to be beyond the acute phase of injury with a minimum of a three-month period since injury. Our clinical experience suggests that patients are medically stable at this time but often struggling with persisting cognitive and emotional sequelae of mmTBI. By applying the technique in patients with mild to moderate severity the likelihood of intact neural circuits undergoing a robust adaptive neuroplastic change is maximized. An ongoing controversy in the TBI literature is the high rate of postconcussive symptoms that occur in healthy non-TBI populations, calling into question the validity of these symptoms. By simultaneously recruiting healthy controls as a comparator group, we will be able to demonstrate that there are clear cognitive control deficits in mmTBI patients, and whether tDCS is more or less efficacious in a clinical versus nonclinical population.

*tDCS is effective in clinical studies at UNM.* Our group at UNM has experimented with a number of different variables regarding tDCS to determine optimal effects on attention and learning. Using a paradigm of a threat detection task for learning, Clark and colleagues found activation on fMRI in right inferior frontal cortex and right parietal cortex, which were then used as targets for stimulation.

PROTOCOL TITLE: Transcranial direct current stimulation for treatment of deficits after traumatic brain injury.

Higher current densities, up to 2 mA for 30 minutes, applied to these localized networks produced greater increases in learning on the threat detection task in a dose-response manner that were still detectable one hour later (Figure 2). Using the same paradigm, we then demonstrated a prolonged effect on alerting attention with the Attention Network Task after just one 30 minute session of anodal tDCS to right inferior frontal cortex. Variables that most enhanced task performance were exposure to task stimuli during stimulation and repetition of the various stimulus response contingencies. Therefore there is ample experience at our center to conduct intensive studies of tDCS for mmTBI and to determine optimal stimulation paradigms and patient characteristics. In addition, the PI of the current project has written several reviews of safety of neuromodulation therapies in various patient populations and treated hundreds of clinical patients with electrical stimulation.

*Established expertise in neuroimaging of TBI.* Our group has also been very active in the longitudinal study of TBI patients, utilizing multimodal neuroimaging and neuropsychological testing to assess biomarkers of injury and recovery. In adult and pediatric mTBI populations we have documented deficits in attention, post-traumatic symptoms, diffusion tensor abnormalities, neurometabolites, and fMRI differences, both in the semi-acute phase and in the chronic phase (4 months post-injury). We have used fMRI to examine attentional dysfunction in patients with TBI, observing decreased activation in both sub-cortical and cortical networks. The PI of this project has been providing clinical care for brain injured patients on an inpatient neurosurgical service and in an outpatient neuropsychiatry clinic for the past five years, and has ample experience with retention, characterization, and treatment of this clinical population. MRI sequences for characterization of TBI may be obtained as part of baseline and post-stimulation assessment in a subgroup of mmTBI subjects. The advantage of obtaining neuroimaging in this study is three-fold: 1) structural abnormalities may affect current flow and alter the effectiveness of TDCS; 2) TDCS has been shown by our group to increase glutamate under the anodal electrode, and use of MRS to characterize neurometabolite flux before and after stimulation could add important evidence to this theory; 3) mmTBI may cause functional brain activation abnormalities independent of structural lesions that can be correlated and localized with EEG.

*EEG is a candidate biomarker for tDCS effect in TBI.* Co-Junior investigator [name] has extensive experience analyzing EEG measures of frontal midline theta band synchrony in various populations as a phenomenon underlying cognitive control. Task-related EEG abnormalities have been found to distinguish patients with mmTBI from healthy controls, and correlate with executive dysfunction. PI [name]'s co-occurring study will investigate whether functional EEG variables such as theta band phase synchrony will correlate with the common disturbances of cognitive control during the semi-acute stage of recovery from mmTBI. We will apply this technique to investigate whether chronic post-concussive symptoms are associated with these same EEG abnormalities, and what effect tDCS may have to increase frontal theta synchrony.

### 3. Study Design

This study is a randomized placebo-controlled clinical trial. Investigators will be blinded to the type of stimulation given (sham versus active) through use of a computer-assisted pre-programmed tDCS stimulator. Subjects will be blinded to sham versus active through the use of low-current (up to 0.2 mA) sham stimulation, which provides a tactile sensation similar to active 2.0 mA stimulation. Ramping up and down the current at the beginning of stimulation also prevents subjects from distinguishing sham from active. The duration of an individual subject's participation in the research may range up to 1 year. The duration anticipated to enroll all subjects is 3 to 4 years. The expected duration for the investigators to complete the study (complete analysis) is 5 years.

**PROTOCOL TITLE:** Transcranial direct current stimulation for treatment of deficits after traumatic brain injury.

### **Inclusion and Exclusion Criteria**

Human participants who have suffered mmTBI (ages 18-55) will be recruited from the UNM Hospital ED and from other local Emergency Departments via CTSC patient recruitment services. Healthy controls will be recruited from the greater Albuquerque area via flyers and online ads. If a participant shows interest in participating in our study, a brief prescreening will be done over the telephone prior to initiating informed consent procedures. The prescreening procedures will assure that each potential participant meets study inclusion and exclusion criteria. If, after prescreening, the patient remains interested and eligible, the project will be described in great details and the potential participant and their caregivers will be invited to come to the investigation site to ask questions prior to providing consent. Consent forms will be provided, as well as forms that again describe the study procedures and potential risks in detail. If potential participants are unsure about participation, they will be given a copy of the consent form with our contact information and be invited to call if they decide to participate. Once informed consent is obtained and the appropriate forms signed, the complete procedures of the study, as described in the consent forms, are provided to prospective subjects. We review the forms, and file them away in a locked file cabinet in a locked office, away from any material with personal or sensitive study data.

### **Inclusion Criteria**

Patients seen the emergency department (ED) will be enrolled in this study if they 1) are aged 18-55, 2) have suffered a TBI with documented evidence of loss of consciousness (LOC) which was less than 24 hours, 3) were injured between 3 months and 15 years ago, 4) received a Glasgow coma scale (GCS) score of between 9 and 15 upon ED admission, 5) experienced less than 1 week of post-traumatic amnesia (PTA), and 6) have post-traumatic cognitive symptoms as evidenced by endorsing at least 1 out of 4 cognitive symptoms on the Neurobehavioral Symptom Inventory (NSI), a measure of post-traumatic symptoms from the NIH Common Data Elements, and 7) have been on stable doses of any psychotropic medications for the past 2 months.. Healthy controls will be between the ages of 18-55.

### **Exclusion Criteria**

Potential participants will be excluded from participation in this study if there is 1) a prior history of other neurological disease or any history of seizures, 2) history of psychosis 3) history of current or recent (within two years) substance/alcohol dependence, 4) any discontinuity in skull electrical conductivity (i.e., unhealed burr holes in scalp) or artificially constructed (metal or plastic) craniotomy cover; 5) presence of any implanted electrical device (e.g. pacemaker), 6) recent medical instability (within three weeks), 7) any condition that would prevent the subject from completing the protocol, 8) appointment of a legal representative, as assessed via direct inquiry of the subject and a designated trusted other. Because our population will have only mild to moderate TBIs, and be well beyond the subacute phase of injury (> 3 months), ongoing complications from the injury itself such as skin infection, bleeding, ischemia, swelling, increased intracranial pressure, seizures, and hyponatremia will be extremely unlikely. However, these would be considered exclusionary criteria if present over the previous three weeks prior to enrollment. Adults unable to consent, individuals who are not yet adults (infants, children, teenagers), pregnant women, and prisoners are specifically excluded from the study. Persons not fluent in English will be excluded, as the neuropsychological test batteries are administered in English.

PROTOCOL TITLE: Transcranial direct current stimulation for treatment of deficits after traumatic brain injury.

TARGETED/PLANNED ENROLLMENT: Number of Subjects			
Ethnic Category	Sex/Gender		
	Females	Males	Total
Hispanic or Latino	26	38	64
Not Hispanic or Latino	38	58	96
Ethnic Category: Total of All Subjects *	64	96	160
Racial Categories			
American Indian/Alaska Native	4	4	8
Asian	2	2	4
Pacific Islander	2	2	4
Black or African American	2	2	4
White	46	66	112
Other races	10	16	26
Two or more races	2	4	6
Racial Categories: Total of All Subjects *	64	96	160

PROTOCOL TITLE: Transcranial direct current stimulation for treatment of deficits after traumatic brain injury.

#### 4. Study Timelines

GOAL	YEAR 1	YEAR 2	YEAR 3	YEAR 4	YEAR 5
Project Progress	Human Subjects Review Board approval completed  Equipment purchased  Biostatistical training completed  Clinical Supervisor and Research Assistant training completed  Begin participant recruitment (targeted enrollment of 10 active tDCS patients and 10 controls)  Progress reported to Human Research Protections Office (HRPO), PI, and NIH.	Recruited 20 active tDCS patients and 20 controls  Preliminary data analyses on tDCS effects completed, in preparation for NIH grant submission  Progress reports submitted to to HRPO, PI and NIH	Recruited 10 active tDCS patients and 10 controls  Completed preliminary data analyses of group differences in tDCS effects across groups  Progress reports submitted to to HRPO, PI and NIH	Progress reports submitted to to HRPO, PI and NIH  Complete all data analysis	Progress reports submitted to to HRPO, PI and NIH  Closure Report submitted to HRPO

PROTOCOL TITLE: Transcranial direct current stimulation for treatment of deficits after traumatic brain injury.

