## 6. Research Setting

All testing, analytical, and research activities will take place at the Clinical Core, UNM Center for Brain Injury Recovery and Repair, located in Domenici Hall, MIND Research Network.

Subjects will be identified and recruited from the UNM ED and other local EDs via the CTSC patient recruitment service, as well as coordination with ED providers and posted advertisements. Healthy controls will be recruited through online advertisements, word of mouth and flyers. As the only Level 1 trauma center for the state of New Mexico and the community hospital for Bernalillo County and the city of Albuquerque, which is the most populous city in the state, UNM treats the majority of TBIs presenting in the state. Approximately 10,000 New Mexicans receive treatment for a TBI in hospitals annually, and the majority of these injuries (~9000) are mild in nature; therefore, recruiting 80 TBI subjects and 80 healthy controls over 3 years is felt to be a feasible goal.

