### Experimental Design and Methods

**Participants:** Eighty TBI subjects will be recruited for this study, all having suffered mild or moderate TBI (mmTBI, as defined before) at least 3 months prior to study enrollment, but not more than 15 years prior to enrollment. 80 age- and sex-matched healthy controls will be recruited. All participants will be 18-55 years of age. We will expect to screen approximately 120 patients with mmTBI in order to reach our goal of 80 TBI subjects. The experimental pre-post, double-blind design is graphically displayed. It includes randomization of TBI patients to either a left-sided active transcranial direct current stimulation (tDCS) protocol, or sham treatment group to foster isolation and identification of any tDCS treatment effects. To enhance our statistical power to identify predictors of treatment response in mmTBI patients, 40 TBI subjects and 40 controls will be assigned to each group: left-sham and left-active.

**Recruitment:** Recruitment primarily will be through the UNM Hospital Emergency Department (ED) (the only Level 1 trauma center in New Mexico). The UNM Health Sciences Center (HSC) Clinical and Translational Science Center (CTSC) Participant Recruitment Service (PRS) for Clinical Research will monitor ED intake records for patients who meet criteria once released from the hospital, then notify the study team of these cases. A second means of recruitment will involve direct referrals from UNM and non-UNM ED physicians and/or referrals from any clinic in the Albuquerque metropolitan area, via the distribution of flyers and calls to clinical directors to publicize the study. A third means of recruitment will involve information listed on the UNM CBRR and MRN websites, and posted flyers.

**PROTOCOL TITLE:** Transcranial direct current stimulation for treatment of deficits after traumatic brain injury.

[figure not shown]

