## **21. Compensation**

Each of the 80 participants will receive \$20/hr in the form of cash cards for taking part in the study. This is felt to be a fair amount that is not coercive and will help decrease attrition for this study which involves many visits.

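### The recruitment timeline and both compensation statements cover 80 participants while the design enrols 160, and the timeline finishes all analysis before the last 1-year follow-up is due

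*Combined protocol and SAP*

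**What the plan says.** **Enrolment in the timeline.** Section 4 lists "targeted enrollment of 10 active tDCS patients and 10 controls" for Year 1, "Recruited 20 active tDCS patients and 20 controls" for Year 2 and "Recruited 10 active tDCS patients and 10 controls" for Year 3. No recruitment is listed for Years 4 or 5.

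**Enrolment in the design.** Section 10 (Study Procedures, Aim 1.1, Participants) plans 80 TBI subjects and 80 matched healthy controls, and states that "40 TBI subjects and 40 controls will be assigned to each group: left-sham and left-active". Section 6 (Research Setting) says that "recruiting 80 TBI subjects and 80 healthy controls over 3 years is felt to be a feasible goal". The planned enrolment table under the eligibility criteria has a stated total of 160.

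**Compensation.** Section 21 begins "Each of the 80 participants will receive". The same figure of 80 appears at the end of Section 10, under Aim 2.3.

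**Timing.** Section 4 puts "Complete all data analysis" in Year 4 and leaves only progress reports and the closure report for Year 5. Section 3 (Study Design) says "The duration anticipated to enroll all subjects is 3 to 4 years" and expects complete analysis to take 5 years. Section 10 (Aims 1.2 and 2.2) has TBI subjects contacted 6 months and 1 year after stimulation.

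**The concern.** The enrolment total drives the budget, the staffing and what each comparison can show. Here it takes two values, one twice the other, and the word 'controls' does not settle which people the smaller figure leaves out. The healthy cohort has a stated purpose: Section 2 (Choice of study population) relies on it to show that cognitive control deficits are present in TBI patients, and to compare the effect of stimulation in clinical and nonclinical groups. The sham TBI arm is the comparator for the primary analysis. A study run to the timeline would lack one or the other.

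The analysis date matters for a different reason. Section 5 names quality of life from baseline to 1 year as a secondary endpoint, and Aims 1.2 and 2.2 rest on the 6-month and 1-year contacts. Closing all analysis before those contacts are finished would lose the latest entrants from the persistence analyses.

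**Working it through.** **1. The design figure (Section 10, Section 6, enrolment table).** (40 TBI + 40 healthy) × 2 stimulation groups = 160. Section 6 gives 80 + 80 = 160. The ethnic rows of the enrolment table give 64 + 96 = 160. These three agree.

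**2. The timeline figure (Section 4).**

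| | Year 1 | Year 2 | Year 3 | Sum |
|---|---|---|---|---|
| Active tDCS patients | 10 | 20 | 10 | 40 |
| 'Controls' | 10 | 20 | 10 | 40 |
| Total | 20 | 40 | 20 | 80 |

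Gap: 160 − 80 = 80 people unscheduled.

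**3. Who is missing, under each meaning of 'controls'.**
- *Sham group.* This is the usage in Section 10 (the randomisation text and the sham description) and in Section 18. The table then schedules 40 active and 40 sham TBI patients and none of the 80 healthy controls.
- *Healthy people.* This is the usage in Sections 2 and 6 and in the participants paragraph of Section 10. The table then schedules 40 active TBI patients and 40 healthy people. It omits 40 sham TBI patients and 40 of the healthy controls.

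The total is 80 on either meaning.

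**4. What the power statement needs (Section 11).** It compares 40 active with 40 sham patients at d = 0.7, so 40 + 40 = 80 TBI patients. Healthy controls do not enter it. Section 11 gives neither alpha nor sidedness. Assuming two-sided 0.05, a two-sample t-test with 40 per arm has 87.1% power, and 34 per arm would give 80%. The stated 80% is matched with two-sided 0.025 (79.9%), or with about 15% attrition at two-sided 0.05 (34 of 40 retained per arm, 81.2%). Even at two-sided 0.01, 80% power needs 50 per arm, or 100 in all.

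**5. When the last 1-year contact falls.** Last contact = enrolment duration + stimulation period + 1 year. Ten consecutive weekdays span about 14 days, and 14/365.25 = 0.04 year. Enrolment is assumed to start on day 1 of Year 1.
- 3-year enrolment: 3 + 0.04 + 1 = 4.04.
- 4-year enrolment: 4 + 0.04 + 1 = 5.04.

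Year 4 ends at 4.00. Year 1 also contains ethics approval, equipment purchase and staff training. If enrolment starts 6 months in (an assumption) and still takes 3 or 4 years, the figures become 4.54 and 5.54.

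**6. Clerical check of the enrolment table, racial rows.**
- Women: 4 + 2 + 2 + 2 + 46 + 10 + 2 = 68, stated 64.
- Men: 4 + 2 + 2 + 2 + 66 + 16 + 4 = 96, as stated.
- All: 8 + 4 + 4 + 4 + 112 + 26 + 6 = 164, stated 160.

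**The case against.** The best defence is that Section 4 is a milestone table and contains no stopping rule, while the enrolment table, Section 6 and Section 10 agree on 160. Read with the randomisation text, 'controls' is the sham arm, and the table then schedules exactly the 40 versus 40 that Section 11 powers. Section 7 supports this: 25 to 30 mild TBI patients a year gives 75 to 90 over 3 years, which fits 80 TBI patients. On this view the table merely leaves out the healthy cohort. On timing, the table ends recruitment in Year 3, so the overlap with the analysis is about two weeks, and Section 3 already allows 5 years.

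Much of this stands. The sham meaning is the likelier one, and the omission most likely concerns the healthy controls. It does not remove the contradiction: half of the planned enrolment has no schedule, and the compensation statements repeat 80. If those 80 are the TBI patients alone, payment of healthy controls is unspecified. The two-week overlap also depends on recruitment closing at the end of Year 3, whereas Section 3 allows a fourth year.

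A reader might infer more than the documents support:
- *That power requires 160.* Section 11 powers 80 TBI patients. Section 10 mentions power when it sets the group sizes, but only for finding predictors of response in TBI patients, and it gives no calculation.
- *That the primary comparison would shrink to 20 versus 20.* Section 4 schedules 40 active patients, so spreading 80 people over four cells contradicts the table itself.
- *That about a quarter of all participants would lack a 1-year outcome.* This sets the 4-year upper limit in Section 3 against a table that stops recruiting in Year 3, and it counts everyone although Aim 1.2 enters TBI subjects for the long-term contacts.

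**Conclusion.** The inconsistency is real. The timeline and compensation cover 80 people and the design enrols 160, a gap of 80. On the likelier reading, the powered TBI comparison is fully scheduled and the healthy comparison is not scheduled at all. On the other reading, the sham TBI arm is missing. The documents do not settle which is meant.

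The Year 4 analysis conflicts with the 5 years in Section 3. It precedes the last 1-year TBI contact by about two weeks with 3-year enrolment and by about a year with 4-year enrolment, if enrolment starts on day 1; a later start with the same duration widens the gap. The exposure is confined to long-term secondary outcomes. The primary endpoint compares scores before and after a stimulation course of about two weeks, and would not be cut off.

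The racial-row sum is a separate clerical slip of 4 women. No analysis is shown to use it.

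**What to change.** - Restate the Section 4 timeline by cell (active TBI, sham TBI, active healthy, sham healthy) so that it totals 160. Carrying the existing 10/20/10 pattern into each cell would give 4 × 40 = 160; the yearly split is for the study team to set.
- Replace 'controls' in Section 4 with the specific group meant.
- Change both compensation statements (end of Section 10 and Section 21) from 80 to 160.
- Place the final analysis after the last 1-year TBI contact and make Sections 3 and 4 agree. With 3-year enrolment from day 1 this falls early in Year 5. With 4-year enrolment the last contact, at about year 5.04, slightly exceeds the 5 years in Section 3, so either the enrolment period or the completion date has to change.
- Correct the racial rows of the enrolment table so that they add to 64 women and 160 in all.

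The cost is protocol wording. If participant payments were budgeted for 80, that line must be raised to match the 160 already planned; the documents do not show the budget.
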